## 3 STUDY OBJECTIVES

### 3.1 Overall Objective

The overarching aim of this research project is to prevent orthopedic implant-associated infections.

### **3.2 Primary Objective**

In this study we aim to investigate if PDT with MAL or methylene blue has an effect on bacterial skin colonization and decreases number of colonizing bacteria to improve skin antisepsis strategies for the prevention of surgical site infections.

In a previous pilot study, we investigated if skin antisepsis can be improved with previous PDT with MAL-induced Pp IX on inguinal skin in 10 participants. We showed a complete sterilization of colonizing skin bacteria at the same day after this treatment. However, orthopedic surgeons are hesitant to perform an arthroplastic surgery after such a treatment due to skin erythema for a few days.

We are entirely convinced about this novel prevention concept but need to identify the optimal irradiation source and the photosensitizer with the ideal balance of antibacterial effect versus skin irritation.

### **3.3 Secondary Objectives**

Effect of PDT on the skin microbiome using molecular techniques.

### **3.4 Safety Objectives**

Evaluation of adverse events

## **4 STUDY OUTCOMES**

### **4.1 Primary Outcome**

Effect of PDT with the MAL-induced Pp IX (group A) and Methylene blue (Ondine NF-031) (group B) in combination with skin antisepsis on bacterial skin colonization on the day of application and on day 0, 1, 3 and 5

- 1.1. To quantitatively evaluate bacterial density and species before and after PDT and skin antisepsis using culture techniques

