## Microbiology

In short, the patient's sample swabs will be streaked out onto Columbia sheep blood agar plate without antibiotics (bioMérieux, Marly-l'Etoile, France), colistin-nalidixic acid (CNA) blood agar (bioMérieux) plate for aerobic cultivation and a Brucella plate (in-house sheep blood agar plates with hemin and vitamin K1) for anaerobic cultivation using GENbag (bioMérieux). Final identification will be done by matrix-assisted laser desorption ionization-time of flight mass spectrometry spectrometry (MALDI-TOF MS) using a Bruker MALDI Biotyper. The amount of bacteria will be semiquantitative described as +, ++, +++ based on growth on agar plates. All cultured microorganisms will be stored in skim milk at -80C° for potential subsequent analysis by whole genome sequencing for analyzing the secondary outcome.

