### **8.3.2 Visit 1 = Day 0 of the study**

#### Group A (MAL group):

On day 0 with [name], a skin scraping of the groin will be performed and sent for microbiological culture. Then, 5% topical methyl aminolevulinate (MAL) as the prodrug for the photosensitizer Pp IX will be applied (5 x 10cm in the right groin) and followed by irradiation of the area with day light.

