### 10.3 Planned Analyses

- As a pilot study, we plan to do descriptive statistics only.
- Categorical data will be tested for differences using Fisher's exact or chi-squared tests.
- Continuous variables will be tested using Wilcoxon rank sum tests.
- Data will be analyzed using Stata® version 14.2 (Stata Corporation, College Station, TX). Two-tailed P-values <0.05 are considered statistically significant.

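### Section 10.3 limits the pilot to description yet sets an unadjusted p<0.05 rule, and the primary outcome in 4.1 names no lead contrast

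*Combined protocol and SAP*

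**What the plan says.** **Outcome.** Section 4.1 defines the primary outcome as the effect of PDT in group A (MAL) and in group B (methylene blue) on colonization of the skin "on the day of application and on day 0, 1, 3 and 5". Its one sub-item reads: "To quantitatively evaluate bacterial density and species before and after PDT and skin antisepsis using culture techniques". The day of application is day 0 (section 8.3.2: "Visit 1 = Day 0 of the study"), so there are four distinct days. Density is an ordinal grade (Microbiology, under 8.2.1): "The amount of bacteria will be semiquantitative described as +, ++, +++ based on growth on agar plates".

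**Analysis.** Section 10.3 opens by confining the pilot to descriptive statistics. The same list then says "Categorical data will be tested for differences using Fisher's exact or chi-squared tests", assigns rank-sum tests to continuous variables, and closes with "Two-tailed P-values <0.05 are considered statistically significant". The synopsis row on statistical considerations and the opening of section 10 repeat the tests without the descriptive limit. The synopsis row on participant numbers and section 10.3.2 repeat the descriptive limit without the tests. Section 10.3.2 describes the primary analysis only as a comparison before and after PDT.

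**Comparator.** Sections 2.5 and 5.2 also set up the untreated contralateral groin as a control. Section 5.2 takes it in every participant; the synopsis takes it in 10; section 7.1.2 takes it in the first 10.

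The documents contain no multiplicity adjustment, testing hierarchy or success rule.

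**The concern.** A purely descriptive study does not need a significance threshold. Once one is written down without limits, it applies to whatever is tested. Here that could be any combination of group, day, measure, swab and comparator.

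Two teams could follow this plan faithfully and report different headline results: one a table of growth rates, the other whichever day or measure fell below 0.05. The second report would look pre-specified. Sections 2.1 and 5.1 make a trial in hip arthroplasty patients depend on promising results, and do not say on which day or measure promise is judged. A chance finding labelled significant could colour that judgement. A lead contrast can be named credibly only before the data are seen.

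**Working it through.** **The plan's own figure.** The only stated figure is the two-sided 0.05 level. For one test it gives an error of 0.05, as expected. The 20 volunteers come without a calculation, so there is no power figure to reproduce.

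**Count of cells (mine; the protocol gives none).** 2 groups x 4 days x 2 measures (4.1) = 16. This treats species as one test, which the protocol does not define. It leaves out the pre-antisepsis scrapings listed in 8.1 and 8.3.3 and the choice between baseline and contralateral groin, either of which would add cells.

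**Independent tests, no true difference anywhere.** Chance of at least one p<0.05 = 1 - 0.95^k:
- k = 4: 18.5%
- k = 8 (one measure): 33.7%
- k = 16: 56.0%, with 16 x 0.05 = 0.8 false positives expected

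**Correlated outcomes.** Swabs from one person are correlated, and the documents give no value. A simulation of 16 rank-sum tests at 10 versus 10 (2,000 runs per setting, equal correlation assumed within each group) gave:

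| Assumed correlation | 16 tests | 8 tests |
|---|---|---|
| 0 | 53% | 29% |
| 0.3 | 47% | 27% |
| 0.5 | 41% | 25% |
| 0.8 | 29% | 21% |

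**Binary outcomes with Fisher's test.** At 10 versus 10 the true size is at most about 1.28% (growth rates tried from 5% to 95%; the maximum is at 50%). Then 1 - (1 - 0.0128)^k is about 5.0% for k = 4, 9.8% for k = 8 and 18.6% for k = 16.

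For 16 cells this gives roughly 19% to 56%. Neither end is a hard limit. Correlated binary outcomes would fall below 19%, and extra swabs or comparators would raise the count. Both calculations treat the two samples as unpaired, as the listed tests do.

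**After the change.**
- One pre-named contrast: 5%.
- The same contrast in both groups, unadjusted: 1 - 0.95^2 = 9.75%.
- Split to 0.025 each: 1 - 0.975^2 = 4.9%.
- Bonferroni over 16 cells: 0.05/16 = 0.0031 per test.

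**What 10 pairs can show on growth versus no growth.** For an exact McNemar test with all discordant pairs in one direction, p = 2 x 0.5^d: d = 5 gives 0.0625, d = 6 gives 0.031, d = 7 gives 0.016. So 0.05 needs at least 6 discordant pairs of 10, and 0.025 needs at least 7. Bonferroni over 16 would need all 10 (d = 9: 0.0039; d = 10: 0.0020).

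**The case against.** The strongest reply is that this is a 20-person, open-label, non-randomized pilot that calls its analysis descriptive in three places, including the primary analysis itself. Section 2.4 ties the next study to sterile cultures after PDT and antisepsis without side effects, not to a p-value. That stands, and it limits the stakes. It does not resolve section 10.3, where the descriptive limit and the significance rule sit in one list.

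Three stronger readings are tempting, and the documents do not support them:
- *The plan runs 16 tests with a 56% false-positive risk.* No number of tests is planned, and 56% needs 16 independent tests with no true difference in any cell.
- *A chance p-value would launch the next trial.* No decision rule uses one.
- *The protocol treats day 0 as the day that matters for surgery.* It does not say so. Section 5.1 schedules the later swabs to learn how long the effect lasts, and erythema lasting a few days is the surgeons' stated worry. Choosing day 0 is a proposal. It fits the same-day sterilization reported from the earlier pilot (synopsis, 3.2) and the sterile-culture condition in 2.4, but the sponsor could justify another day.

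It is also fair to say that a post-antisepsis swab compared with baseline carries the antiseptic's own effect, so a small p-value there may be confounded rather than a chance result. That favours the contralateral groin as comparator. Finally, growth versus no growth discards the grade, although section 3.2 asks about numbers of bacteria. The grades should therefore still be reported.

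**Conclusion.** The point holds as an inconsistency in section 10.3 combined with an open-ended primary outcome in 4.1. If the listed tests were run on all 16 cells, the chance of at least one false positive would be roughly 19% to 56%. That range rests on my count of cells, on no true difference in any of them, and on the assumed correlation and test type. It describes what the wording permits, not what the team has said it will do. With no p-value-based go rule the consequence is moderate. The correction is worth making because it is inexpensive before data are seen and cannot be made credibly afterwards.

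**What to change.** 1. **Section 10.3** (and the synopsis and the opening of section 10): either delete the p<0.05 rule and report estimates with confidence intervals, or restrict the rule to one pre-named contrast.
2. **Section 4.1:** name the lead contrast. One that uses swabs already described is growth versus no growth on the day 0 post-antisepsis swab, PDT groin versus contralateral groin of the same person, analysed as paired data (for instance exact McNemar, with an interval for the paired difference).
3. If it is tested in both groups, use 0.025 in each or a fixed order.
4. Report days 1, 3 and 5, the semiquantitative grades and species descriptively, without significance claims.
5. Reconcile the synopsis and 7.1.2 (control in 10, or the first 10, participants) with 5.2 (all participants). Section 2.7 puts the first ten enrolled in group A, so under the narrower reading group B would have no control swabs for this contrast.
6. Reconcile section 8.3.3, whose text gives day 7 under a heading of days 1, 3 and 5.

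**Cost.** Mostly wording, but section 1.14 makes changes to endpoints or the form of analysis subject to ethics committee approval, so an amendment is needed. No new samples are needed if 5.2 governs; if 7.1.2 does, group B's contralateral swabs must be added. Fewer results can be called significant, and with 10 pairs per group even the lead contrast reaches 0.05 only with at least 6 discordant pairs, which is a reason to prefer estimates with intervals.

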### **4.2 Secondary Outcomes**

Effect of PDT on the skin microbiome using molecular techniques.

### **4.3 Safety Outcomes**

Every PDT is documented as in routine clinics on a standardized protocol in the KISIM database (see appendix 1).

Clinical signs and symptoms after PDT as adverse events. We will distinguish between:

- Mild redness and pain as to be expected (yes/no)
- Advanced redness and pain more than expected (yes/no): adverse event.
  - o “More than expected” is defined, if patients needs to take more than 1 painkiller/day
- Other signs and symptoms not expected (yes/no)

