In a previous pilot study, we investigated if skin antisepsis is improved with previous PDT with the photosensitizer- inducing prodrug 5% topical methyl aminolevulinate (MAL) on inguinal skin in 10 participants. The induced photosensitizer was protoporphyrin IX (inducing a photodynamic effect with 635 nm light source) and we showed a complete sterilization of colonizing skin bacteria after this treatment (Waldmann, Schmid et al. 2020). However, due to skin erythema for a few days after PDT, orthopedic surgeons would be hesitant to perform an arthroplasty surgery after this treatment. Therefore, we aim to have a PDT with less local side-effects (skin erythema).

Ondine's methylene blue based photosensitizer NF-031 is mainly formulated in a primarily hydrophilic carrier, and therefore does not penetrate the stratum corneum over short periods of time, providing potent surface disinfection. According to the company Ondine, we can expect less side effects as with Pp IX. We will also repeat the MAL PDT with day light as a promising light source with expected less side effects such as pain and redness (Wiegell, Haedersdal et al. 2008, Rubel, Spelman et al. 2014).

The aim of this pilot study is to evaluate the effect of PDT with the photosensitizer MAL with and the photosensitizer Methylene blue on colonizing bacteria immediately before surgical skin antisepsis and after it. If we see promising results in this pilot study, we will plan a prospective clinical trial in patients undergoing hip arthroplasty surgery.

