## 2.4 Justification of Study Intervention

PDT enjoys great popularity as it is well tolerated. Therefore, we select this promising treatment to investigate an innovative strategy to improve skin antisepsis in a pilot study. If we see that we have sterile cultures after PDT and skin antisepsis without side effects, we will plan a larger prospective study based on these data.

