**Risks**

- Minimal risk (transient erythema and pain) using PDT (no long-term sequelae). No inflammation seen on histopathology in previous trial

Possible side effects of the PDT are pain in the area of treatment, erythema and edema during and after light treatment (Borgia, Giuffrida et al. 2018). These side effects are self-limiting. We expect less erythema with day-light PDT and with the photosensitizer Methylene blue than with the previously tested MAL induced Pp IX photosensitizer (Waldmann, Schmid et al. 2020).

Since our study interventions (see above) have minimal risks for participants, it is reasonable to conduct this pilot study before starting a larger clinical trial with patients undergoing hip arthroplasty surgery.

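### Less erythema is a stated aim of this second pilot, but 4.3 records redness only jointly with pain, in ungraded yes/no items, and no redness-by-visit summary is planned

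*Combined protocol and SAP*

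**What the plan says.** The protocol gives the reason for a second pilot in 2.1: "due to skin erythema for a few days after PDT, orthopedic surgeons would be hesitant" to operate. Sections 2.1 and 2.3 then state the aim of a treatment with less erythema. The risk paragraph of 2.6 adds: "We expect less erythema with day-light PDT and with the photosensitizer Methylene blue" than with the MAL treatment tested before. The primary objective (3.2) looks for the "ideal balance of antibacterial effect versus skin irritation", and the synopsis says much the same. Section 2.4 makes a larger study depend on "sterile cultures after PDT and skin antisepsis without side effects". The primary outcome (4.1) and the hypothesis (10.1) are bacterial.

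Redness appears among the outcomes only in 4.3, which has three items:
- "Mild redness and pain as to be expected (yes/no"
- "Advanced redness and pain more than expected (yes/no): adverse event"
- "Other signs and symptoms not expected (yes/no"

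The phrase *more than expected* "is defined, if patients needs to take more than 1 painkiller/day". *Mild* and *advanced* have no definition. Section 10.3.5 plans the number of adverse and serious adverse events.

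**The concern.** The earlier pilot already reported complete sterilisation on the day of treatment. What held the approach back was how red the skin became and for how long. A second pilot that seeks less erythema needs a measure of redness that separates slight from marked and shows when it has gone.

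Section 4.3 does not clearly supply one. It joins two symptoms, uses undefined severity words, and sets its one operational threshold on painkiller use, which reflects pain. Section 2.1 also expects less pain with daylight, so a criterion driven by painkillers could improve while redness stayed the same. Two regimens that differ in the severity or duration of redness could look alike in a count of adverse events. The irritation side of the balance in 3.2 would then be poorly described when the next trial is planned.

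**Working it through.** The plan states no figure for redness, so there is nothing to reproduce. The check has three parts.

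**1. Apply the *more than expected* item to four skin findings.** The text allows two readings. Under reading A the painkiller criterion governs the whole item. Under reading B it governs pain only, and *advanced redness* is a separate element.

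| Finding | Painkillers per day | Reading A | Reading B |
|---|---|---|---|
| Slight redness, no pain | 0 or 1 | not met | not met |
| Marked redness, no pain | 0 or 1 | not met | unclear: *advanced* undefined, and the item joins redness and pain |
| Slight redness, pain | more than 1 | met | unclear: pain part met, redness part not |
| Marked redness, pain | more than 1 | met | met, if the redness counts as *advanced* |

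Reading A classifies rows 2 and 3 by pain alone. Reading B leaves both open. Neither yields a redness grade.

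**2. Look for another route to severity and duration.**
- Section 8.1 schedules adverse events on days 0, 1, 3 and 5. Section 8.3.3 repeats this for visits 2 to 4 (its heading gives day 5, its first sentence day 7). Section 12.1.2 lists pain and redness as source data. Presence by visit may therefore exist, but no scale is given.
- The general definition in 9.1, or the withdrawal criterion in 6.3 for known side effects of greater intensity, may bring marked redness in as an adverse event, by ungraded judgement.
- Intensity is specified in 8.2.3.1, and duration in 8.2.3.1 and 9.2, for serious events only. Ordinary erythema is not serious under 9.1.
- Section 9.4 follows ongoing serious events and adverse events of laboratory values or vital signs. A completer still red on day 5 has no stated later assessment.
- Section 10.3 names generic tests but no redness variable, and 10.3.5 counts events.
- The form shown in Appendix 1 carries treatment settings and no redness field. It is only an example, and the eCRF is not available.

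**3. Arithmetic, all inputs assumed.**

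*Logic of the classification.* Suppose marked painless redness occurs in 8/10 v 0/10 and nobody takes more than one painkiller a day. Let q be the share of those cases still recorded as adverse events by judgement. The difference in proportions is 8q/10:
- q = 0: 0/10 v 0/10, 0 points
- q = 0.5: 4/10 v 0/10, 40 points
- q = 1: 8/10 v 0/10, 80 points

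The same skin gives different counts, depending on a judgement that the plan does not state. This shows the mechanism and estimates nothing.

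*Precision of a graded item at 10 per arm* (group size from the synopsis). Exact (Clopper-Pearson) 95% limits: for 0/10 the upper limit is 1 − 0.025^(1/10) = 0.308; 5/10 gives 18.7% to 81.3%.

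For a difference of 8/10 v 4/10, Newcombe's method uses the Wilson limits 0.490 to 0.943 and 0.168 to 0.687:
- lower: 0.40 − √[(0.80 − 0.490)² + (0.687 − 0.40)²] = −0.023
- upper: 0.40 + √[(0.943 − 0.80)² + (0.40 − 0.168)²] = 0.673

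That is 40 points (−2 to 67). A graded item describes redness better but cannot settle a comparison at this size.

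**The case against.** The strongest reply is that this is a descriptive pilot with a bacterial primary outcome and hypothesis, and a safety objective (3.4) limited to evaluating adverse events. Section 4.3 does have a crude mild/advanced split, and its lead-in treats clinical signs after PDT as adverse events. The painkiller criterion may belong to pain alone. Adverse effects are documented at every visit. Grading now also cannot formally test the expectation in 2.6, because that comparison is with the earlier pilot and the documents give no redness grade from it.

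Much of this stands and limits the point. A reader might infer several stronger things that the documents do not support:
- *That redness goes unrecorded, or that its duration is lost because the items are completed once.* Sections 8.1, 8.3.3 and 12.1.2 point to recording by visit, and 4.3 does not say once per participant.
- *That marked painless redness is certain to be missed.* That needs reading A and no use of clinical judgement.
- *That erythema is the sole purpose of the study.* It is one stated aim beside the bacterial one.
- *That 0 to 80 points measures the likely distortion.* It is 8q/10 with chosen inputs.
- *That the painkiller criterion contradicts the NSAR restriction in 6.1.2 and 7.5.* Section 4.3 names no class of painkiller, so the passages need reconciling but do not plainly conflict.

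What the reply does not remove is that no reading of 4.3 gives a grade for redness alone, and no section plans a summary of redness by arm and day.

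**Conclusion.** The point holds as a gap in outcome definition and planned summary. Redness is one side of the balance the pilot seeks, yet it is recorded jointly with pain, its severity words are unanchored, the only operational threshold is painkiller use, and the safety analysis counts events. Marked painless redness may not be classed as more than expected, and pain with slight redness may be.

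The size cannot be derived from the documents. Presence by visit may be recoverable, and yes/no items can partly answer the *without side effects* condition in 2.4. Severity is unlikely to be recoverable afterwards. The conclusion rests on the available text; a redness scale in the eCRF or the full treatment form would narrow it. The change is worth making before enrolment because it is cheap. The primary bacterial analysis is not affected.

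**What to change.** **In 4.3 and the eCRF**, record three separate items: redness (none, mild, moderate, severe, with written anchors, graded by existing staff), pain, and painkiller use. Grade the treated groin before PDT; after PDT on day 0, before the scraping or antisepsis that follows; and on days 1, 3 and 5 before that visit's scraping and antisepsis. Grading the contralateral groin is optional, because 5.2 and 7.1.2 do not clearly set out control follow-up by day.

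**In 10.3.5**, tabulate by arm and visit the proportion with any redness and with moderate or severe redness, with exact 95% intervals, and the last visit with redness (*day 5 or later* if still present). Include participants withdrawn under 6.3 up to withdrawal. They may have the most redness, and 10.3.1 could be read as completers only.

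**Reconcile** the painkiller wording in 4.3 with the NSAR restriction in 6.1.2 and 7.5. No rule is proposed here.

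**State the limits**: descriptive only, open-label grading, sequential non-randomised arms, 10 per arm, possible added redness from repeated scraping and antisepsis, and no redness grade from the earlier pilot in the documents.

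**Cost**: an amendment authorised by the ethics committee under 1.14, and up to five gradings per treated groin (1 before PDT + 1 after + 3 later visits). No extra visits or participants are needed. The remaining downside is an unblinded visual grade with wide intervals.
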